8. INTERVENTION DISCONTINUATION

The research team has the right to ask any participant to leave an intervention session or to discontinue participation in the study to protect the safety of the participant or others in the study.

Reasons that a participant would be asked to leave an intervention session or discontinue participation include:

- Attending sessions or visits impaired or inebriated
- Behaving in ways that are disruptive to others or endanger safety
- It no longer becomes physically safe for a participant to continue in the study.
 - One Serious Adverse Event clearly indicated to be related to the intervention OR
 - More than 3 non-serious AE indicated to be related to the intervention and not reasonably remediable.
 - Participants will be discontinued from the study if they experience complications that could endanger their pregnancy or infant.
- The funding sponsor also has the right to stop the study at any time.

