2. BACKGROUND AND RATIONALE

2.1 Background on Condition, Disease, or Other Primary Study Focus

Prevalence of OUD among pregnant and parenting women in NH is high and costs of untreated OUD are high. Perinatal OUD is described as a national public health epidemic, and NH is no exception.⁸ Roughly 40% of recent opioid overdose deaths in the state were women, and 21% of pregnancy-associated deaths between 2013-2015 were attributed to overdose. An estimated 8-10% of deliveries in NH are affected by perinatal OUD. Rising prevalence rates indicate that NH can anticipate as many as 1,000 infants born with prenatal opioid exposure each year. Perinatal OUD is associated with increased morbidity and mortality for both mother and infant due to infectious disease, higher rates of prematurity and pregnancy complications, low birth weight, neonatal abstinence syndrome (NAS), and social stressors such as homelessness, poor nutrition, and criminal justice involvement. In 2012, nearly 22,000 neonates in the U.S. were born with NAS, translating to one neonate born every 30 minutes and resulting in \$1.5 billion in hospital charges nationwide. Prenatal substance exposure and untreated postpartum maternal substance use are associated with developmental disorders and risk of adverse childhood experiences for children, which are strong predictors of later adolescent and adult substance use disorders and related health consequences.

The current standard of care for treatment of OUD during pregnancy is medication for opioid use disorder (MOUD) with methadone or buprenorphine. Evidence indicates buprenorphine improves neonatal outcomes compared with methadone in terms of lower NAS risk, shorter NAS treatment duration and mean length of hospital stay, higher mean gestational age, and greater weight, length, and head circumference at birth. Medication is most effective in combination with counseling, care management, and psychosocial support to address the complex array of individual and social factors that can adversely impact treatment compliance and the health and wellbeing of women and their children. Expansion of MOUD in obstetric settings for pregnant and parenting women with OUD is a targeted priority of the NH State Targeted Response (STR) to the opioid crisis.

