We have developed a safety protocol (overseen by Drs. [name] and [name]) to ensure strict attention to safety for women participating in the yoga intervention. As with other gentle yoga protocols, the safety protocol will include specific directions by the Intervention Instructor that participants do not have to partake in any of the poses or activities that feel uncomfortable, and adjustments will be made as needed to minimize discomfort for those participants that would like such adjustments. Lead Instructor [name] has over six years of experience leading trauma-sensitive yoga protocols with pregnant incarcerated women, a vulnerable population similar to that for the proposed project.

The Lead Instructor will complete the Session Event Checklist after each intervention session to denote any adverse events (non-serious and serious) that take place during the intervention sessions. Participants will complete the Intervention Experience Form at the end of each session to document experience of any adverse events including physical experiences (e.g., shortness of breath, pain, increased or decreased infant movement, or other discomfort experiences during the session) and psychological experiences (e.g., emotional flooding, uncontrollable crying). At the end of each intervention week, all participants will also complete a Weekly Monitoring Form that will include items related to any additional experience of adverse physical or psychological events. The project coordinator will administer the Weekly Monitoring Form by telephone or e-mail.

In the event that a study participant lapses or relapses during the study period, cases will be handled on an individual basis, which may be largely determined by the procedures of the partner maternity care practice in terms of preference for ongoing care. A lapse/relapse will not necessarily lead to participant discontinuation in the study.

Treatment as Usual. Treatment as usual is operationalized as the integrated medication assisted treatment being provided at the partner practice as part of the New Hampshire State Targeted Response 21st Century Cures initiative. Such treatment includes medication for opioid use disorder, individual and/or group counseling, and case management.

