6.2.5 Follow-up Visit

All study participants will be followed until 3 months postpartum.

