9.3 Definition of Populations

We will use an Intent to Treat model that includes all participants who complete a baseline assessment.

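### Section 8's complication rule, as worded, ends study participation rather than the yoga sessions, contrary to the plan to follow every woman to 3 months postpartum

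*Combined protocol and SAP*

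**What the plan says.** Section 8 (Intervention Discontinuation) gives the research team a power over every woman enrolled, in these words: "leave an intervention session or to discontinue participation in the study to protect the safety of the participant or others in the study". It therefore names leaving a session and leaving the study as separate actions, but does not say which trigger leads to which.

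The triggers include "Attending sessions or visits impaired or inebriated", disruptive or dangerous behaviour, and participation no longer being physically safe. Three sub-bullets sit under the physical-safety item. The first two require adverse events related to the intervention: one serious event, or more than three non-serious ones that cannot reasonably be remedied. The third is "Participants will be discontinued from the study if they experience complications that could endanger their pregnancy or infant". It is mandatory, asks for no link to the intervention, and names no arm.

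Elsewhere the protocol says:

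- Section 6.2.5: "All study participants will be followed until 3 months postpartum".
- Section 9.3: "We will use an Intent to Treat model that includes all participants who complete a baseline assessment".
- Section 5.1, on treatment as usual (TAU): "Such treatment includes medication for opioid use disorder, individual and/or group counseling, and case management". There is no yoga in that arm.
- Section 5.1, on relapse: "A lapse/relapse will not necessarily lead to participant discontinuation in the study". Section 7.1 repeats this.
- Sections 6.2 and 10.1: both primary outcomes come from chart review and from self-report, and the chart measures run to 3 months postpartum.
- Section 9.6: the primary GEE uses the 8-week and the 3-month postpartum time points.

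**The concern.** A safety rule should stop the exposure that might be unsafe. This one, read literally, stops the woman's participation in the trial. Surveys and chart review pose no physical hazard, so ending them adds nothing to the protection gained by stopping yoga.

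At stake are the outcomes of randomised women after a post-randomisation event that may itself be related to retention in treatment or to opioid use. Section 9 states no method for missing outcomes, and a GEE fitted to the available observations generally needs missingness unrelated to outcome once the model's covariates are accounted for. Safety data are also involved. Section 7.3 has adverse events recorded whether or not they relate to the intervention, and section 6.1 schedules them through 3 months postpartum. A woman withdrawn for a pregnancy complication is one whose later events matter most.

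The trigger is foreseeable. Section 2.1 associates perinatal opioid use disorder with "higher rates of prematurity and pregnancy complications", though it gives no rate.

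**Working it through.** **1. The texts side by side.**

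- *Section 8 against section 6.2.5.* One says that women with certain complications leave the study; the other that all are followed to 3 months postpartum. Unless discontinued is taken to mean something less than leaving the study, both cannot be carried out for the same woman. This conflict is direct.
- *Section 8 against section 9.3.* Membership of the intent-to-treat set is fixed by completing baseline, so a woman discontinued later is still in it. There is no conflict of definition. The link is indirect: she is in the set, but may have no later outcome to analyse.
- *What happens to data collection.* No section says that surveys or chart review continue after discontinuation, and none says that they stop.

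**2. The plan's own figures (section 9.2).** Inputs: 150 recruited, 20% attrition, equal allocation, two-sided 0.05, within-person correlation 0.5, three time points.

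- Evaluable: 150 × 0.80 = 120, or 60 per arm.
- Weeks abstinent, 0.52 SD: power = Φ(0.52 × √(60/2) − 1.96) = Φ(0.888) = 81.3%.
- Retention, 60% against 79.2%: the design factor is (1 + 2 × 0.5)/3 = 0.667, so the effective size is 60/0.667 = 90 per arm. Power is Φ[(0.192 × √90 − 1.96 × √(2 × 0.696 × 0.304)) / √(0.6 × 0.4 + 0.792 × 0.208)] = 80.5%.
- The other two binary scenarios give 79.8% (70% against 87%) and 80.3% (80% against 94%).

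The stated 80% reproduces.

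**3. What withdrawals could cost in power.** The documents give no complication rate, so the rates below are assumptions. Each 1% of women affected is 0.01 × 150 = 1.5 women, against an attrition allowance of 0.20 × 150 = 30. If the withdrawals fall within that allowance, power does not change. If a share x comes on top of it, n per arm = 150 × (1 − 0.20 − x)/2:

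| Assumed x | n per arm | Power, retention 60% vs 79.2% | Power, 0.52 SD |
|---|---|---|---|
| 0 | 60 | 80.5% | 81.3% |
| 5% | 56.25 | 77.9% | 78.7% |
| 10% | 52.5 | 75.0% | 75.9% |
| 15% | 48.75 | 71.8% | 72.8% |
| 20% | 45 | 68.3% | 69.4% |

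The table treats a withdrawn woman as contributing nothing. That is pessimistic: she contributes what was collected before she left, and her chart data may still be available.

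**4. Direction of any bias.** Take 75 women per arm, no true effect, and 80% abstinent in each arm (the TAU rate assumed in section 9.2), which is 60 of 75. The losses below are assumed.

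- One non-abstinent MMORE woman lost, none in TAU: 60/74 = 81.1%, a shift of +1.1 points.
- One abstinent MMORE woman lost, none in TAU: 59/74 = 79.7%, a shift of −0.3 points.
- One non-abstinent woman lost in each arm: 60/74 − 60/74 = 0.

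The sign depends on who is lost and in which arm. The documents settle neither.

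**The case against.** Several points on the other side are sound.

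- *Only yoga was meant.* The heading, the physical-safety item above the bullet and its two intervention-related neighbours all support this. A reader might infer that the protocol expressly requires TAU women to be removed. It does not: that follows only from the sentence being unqualified. But nothing limits it to MMORE either, and staff following it literally would end participation.
- *Intent to treat is intact.* A reader might infer that the rule contradicts the intent-to-treat definition. It does not, because the woman stays in the set. What stands is possible missing data.
- *Chart data may survive.* Section 6.2 takes chart measures from routine care records, reviews them at 3 months postpartum, and keeps the linking code until collection and analysis are complete. Discontinuation by the team is not withdrawal of consent. This may protect much of the primary data, but no section says that chart review goes on, and self-report has no such safeguard.
- *Other documents may cover it.* Section 7.4 refers to a Data Safety and Monitoring Plan for details of adverse-event follow-up. That plan and the consent pages were not available for this review, and either might settle the matter.
- *There can be a reason to stop surveys.* Section 7.3 recognises that assessments may cause discomfort. After a pregnancy loss, sparing a woman questionnaires is reasonable in either arm. That argues for discretion over surveys, not for a blanket exit.
- *The impairment trigger is softened.* It is discretionary, relapse does not necessarily end participation, and section 7.1 describes helping a disruptive or hazardous woman leave the room. A reader might infer that the plan discards relapsing MMORE women and so flatters the intervention. The documents do not support that.

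**Conclusion.** The point holds as one of wording with a possible consequence for the data. Section 8, as written, ends study participation for pregnancy or infant complications whether or not they relate to the intervention, with no limit by arm. This contradicts section 6.2.5. The intent-to-treat set is unaffected. Outcomes after discontinuation are at risk only if discontinuation also ends collection: self-report first, chart measures possibly.

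The size cannot be estimated. The documents give no rate of qualifying complications or of discontinuation, and that perinatal opioid use disorder raises complication rates in general does not show how often this rule would be met. The power losses in the table hold only if withdrawals exceed the 20% allowance. It would be going too far to say that the comparison will be biased towards MMORE: nothing shows that complications differ by arm, and balanced losses may leave no bias. The change is still worth making, because uncollected follow-up may not be recoverable later.

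**What to change.** Reword section 8 so that its triggers stop the sessions or the intervention, not study follow-up. Then state that:

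- chart review to 3 months postpartum continues unless the woman withdraws consent;
- remote surveys (online, phone or mail) continue where appropriate, with discretion after pregnancy loss or severe complications;
- she is analysed in her assigned arm;
- discontinuations are reported by arm and reason.

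This takes three or four sentences in section 8 and one line in the results tables. Chart review at 3 months postpartum and the remote survey options are already planned in section 6.2. Sample size and stated power do not change, and the safety protection remains because the intervention still stops. The downside is slight extra follow-up and reporting work.

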9. STATISTICAL CONSIDERATIONS

9.1 General Design Issues

Study Type: Interventional

Estimated Enrollment: 150 participants

Allocation: Randomized

Intervention model: 2-group parallel assignment

The study is a randomized, controlled and blinded efficacy trial comparing Treatment as Usual (TAU) to the Mindful Moms yoga-mindfulness intervention as an adjunct to TAU (MMORE + TAU)

The primary outcomes are MOUD treatment retention and opioid abstinence.

Secondary outcomes include frequency and quantity of other substance use, depression, anxiety, stress, mindfulness, pain perception, and quality of life.

Data collection will occur by way of clinical record review and participant self-report. Self-report assessment surveys will be completed at: baseline, post-intervention, and 3 months postpartum.

9.2 Sample Size and Randomization

Sample Size.

Aim 1: For the longitudinal models of binary outcomes (abstinence, retention), assuming a within-person correlation of 0.5, there will be 80% power to detect difference between arms in the proportion retained at the 3 timepoints if the average percentage retained in the TAU arm is 60%, and the average percentage retained in the MMORE arm is 79.2%. Similar power is obtained if the TAU arm has a retention percentage of 70% while the MMORE arm has a percentage of 87% across the three timepoints. In terms of comparing abstinence longitudinally, there will be 80% power to detect a difference between arms in the percentage abstinent at the 3 timepoints if the average percentage abstinent in the TAU arm is 80% while in the MMORE arm is 94%. Power for the comparison of number of weeks abstinent during the 8-week intervention period will be 80% (at the two-sided 0.05 significance level) for differences between arms that are 0.52 times a standard deviation or more. Analyses testing for differences between arms in changes between baseline and 8-weeks, will have 80% power to detect differences that are 0.40, 0.52, and 0.61 times a standard deviation, assuming within-person correlations of 0.7, 0.5, and 0.3, respectively. We will aim to recruit 150 participants to allow for attrition (20%).

Aim 2: For examining mediation/mechanistic effects at the individual-level from longitudinal data via parallel process growth models (paths from treatment assignment to individual-level slope of mediator to individual-level slope of outcome), with 120 individuals, there will be 80% power to detect indirect effects comprised of a small-medium effects of the intervention arm on latent slope of mindfulness (defined as a correlation of 0.25 between variables or equivalently as explaining 6% of the variance in the latent mindfulness slope) and a medium effect of the slope of mindfulness on the slope of the outcome (defined as a correlation of 0.36 or equivalently as explaining 13% of the variance of the outcome). For examining mediation/mechanistic effects at the weekly level, power is less clear. Although DSEM combines aspects of more familiar modeling techniques, it is new and thus limited information is available on determining power for such models. In one set of simulation studies, good model performance was observed for several models differing in complexity for a sample size of 200 individuals with a number of observations per individual ranging from 20-200, and good model performance for all but the most complex models for smaller sample sizes. Thus, with data from 120 individuals contributing up to 8 observations each, we expect to have enough data to accomplish the aim of understanding the mechanisms underlying the intervention effects of MMORE. We will conduct weekly assessments to minimize participant burden. This strategy will still allow us adequate sampling frequency to track changes in outcome measures over the course of treatment. The power

calculations for the mechanistic effects were based on individual-level latent slope variable estimates and are thus not affected by a change to the number of indicator variables for the latent slope variables (reduced from 70 daily assessments to 8 weekly assessments). Power calculations for the dynamic SEM models are approximate and were not specifically based on having daily assessments per individual so will also not change.

Aim 3 is exploratory and not powered.

Treatment Assignment Procedures

Randomization will be conducted via permuted blocks. Once 8-10 participants have enrolled, an intervention will commence for that cohort. The randomization block size would be random, with blocks of size 4, 6, and 8. We plan ongoing recruitment and to start a new group approximately every 8 weeks.

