6.2.2 Enrollment, Baseline, and/or Randomization

Enrollment

In this study, the enrollment date will be the date that all of the screening criteria were met, and the individual consents to participate.

Baseline Assessments

Participants will complete the baseline assessment upon consenting to participate in the study. The project coordinators will administer the baseline assessment to the participant through a secure online survey. For participants who do not wish to complete the survey online, the project coordinator will arrange for either a phone interview with the participant to complete the survey or will mail the participant the survey along with a self-addressed and stamped envelope for the participant to return the survey. Both forms of the assessment will be coded with a unique study ID.

Randomization

Following baseline completion, participants will be randomized to condition by the lead project coordinator. The lead project coordinator will meet via phone with participants assigned to the MMORE condition to explain the condition. Participants in the MMORE condition will receive a secure password-protected access to the digital companion features.

Randomization will be conducted via permuted blocks. Once 8-10 participants have enrolled, an intervention will commence for that cohort. The randomization block size would be random, with blocks of size 4, 6, and 8. In thinking about how best to implement our group randomization plan in the context of the reality of recruitment of this high-risk target population, we have developed a plan of ongoing recruitment and starting a new group at least every 8 weeks. With a conservative recruitment

rate of 12 participants per month, we do not anticipate a good deal of differential lag-time between recruitment into the study, completion of baseline, randomization, and start of a new group.

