9.6 Data Analyses

Aim 1

Primary analysis: The difference between treatment arms with respect to likelihood of opioid abstinence and remaining in treatment will be evaluated by logistic generalized estimating equations (GEE). Since these binary outcomes will be evaluated at the 8-week as well as the 3-month postpartum time points, these GEE models will account for the non-independence of repeated measurements within individual. An indicator of treatment arm, time point, as well as an interaction between treatment and time point will be included as predictors in the model along with baseline covariates. Significant differences between the arms will be tested via contrasts involving the treatment*time point interaction term that compare the outcomes at each time point.

The impact of *MMORE* on treatment retention (number of weeks retained) will be evaluated via two-sample t-test if the distribution appears symmetric, but a non-parametric Wilcoxon rank sum test will be used otherwise.

Aim 2

Primary analysis: Analyses of mechanisms of effect of *MMORE* will be performed via parallel process growth models fit via structural equation models, and mediated effects between treatment assignment and outcome will be examined for the following mediator-outcome pairs: craving-abstinence, mindfulness-craving, mindfulness-treatment retention, depression-treatment retention, anxiety-treatment retention, stress-treatment retention, and mindfulness-pain. Since each mediator and outcome variable will be collected at multiple time points, latent intercept and slope effects can be estimated (as in latent growth curves). The parallel process growth models then examine mediation of the effect of an individual-level variable (treatment assignment) on the latent slope of the outcome variable by the latent slope of the mediator variable. For each mediator-outcome pair, a parallel process growth curve model will be fit including both the direct effect of treatment assignment to *MMORE* on the latent slope of the outcome, as well as the indirect effect of *MMORE* on slope of the outcome through the slope of the mediator. Estimates of path coefficients for each individual path as well as of the indirect effect along with a 95% bootstrap confidence interval will be obtained.

To examine these associations we will implement a newly developed modeling strategy called dynamic structural equation models (DSEM). DSEM like non-dynamic SEM are a modeling

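### Section 9.2 claims 80% power for a difference averaged over three time points, but Section 9.6 tests two time points one by one with no success rule, giving about 62–65% power per contrast at 60 per arm

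*Combined protocol and SAP*

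**What the plan says.** **Section 9.2 (Aim 1).** The plan claims "80% power to detect difference between arms in the proportion retained at the 3 timepoints if the average percentage retained" is 60% under TAU and 79.2% under MMORE, assuming a within-person correlation of 0.5. It claims similar power for retention of 70% against 87%, and 80% power for abstinence of 80% against 94%. Each pair is an average over three time points. Recruitment is 150, to allow for 20% attrition.

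**Section 9.6 (Aim 1, primary analysis).** The model is a logistic GEE with arm, time point, their interaction and baseline covariates. It has two time points: "Since these binary outcomes will be evaluated at the 8-week as well as the 3-month postpartum time points". The tests are "contrasts involving the treatment*time point interaction term that compare the outcomes at each time point". No contrast averaged over time is named, no time point is given priority, and nothing says whether one or both must be significant. Under the same primary analysis, the effect of MMORE "on treatment retention (number of weeks retained) will be evaluated via two-sample t-test if the distribution appears symmetric", with a rank-sum test otherwise. That test is not ranked against the GEE contrasts.

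**Assessment times.** Section 9.1 says "Self-report assessment surveys will be completed at: baseline, post-intervention, and 3 months postpartum", and the schedule in 6.1 agrees. Section 6.2.2 says "Following baseline completion, participants will be randomized to condition by the lead project coordinator".

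**The concern.** A power statement belongs to one particular test. An average over three correlated visits is more precise than a comparison at one visit, so power computed for the average overstates the power of a single-visit contrast. Here the test described in 9.2 is not among the tests listed in 9.6. The third visit appears to be the pre-randomisation baseline, which treatment cannot affect.

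The missing success rule makes this worse. With two contrasts per endpoint, two endpoints and an unranked weeks-retained test, a reader cannot tell what result counts as success, and so cannot tell which power or which false-positive rate applies. If the rule is settled only after the data are seen, a positive result on any one of these tests could be presented as the primary finding.

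**Working it through.** **Inputs**

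- 150 recruited less 20% = 120, or 60 per arm (9.2; equal allocation in 4.3). Section 9.2 does not state 60 per arm for Aim 1, but this is the number that reproduces its 80%.
- Within-person correlation r = 0.5 (9.2).
- Pairs of rates: 60 vs 79.2%, 70 vs 87%, 80 vs 94% (9.2).
- Two-sided alpha 0.05. Section 9.2 states this only for weeks abstinent; it is assumed here for the binary endpoints.
- Assumption: the stated difference holds at every visit tested. No covariate adjustment.

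**Formulas**

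Effective number per arm for an average over k visits: n_e = n·k / (1 + (k − 1)r).

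Power = Φ[(|p2 − p1| − 1.96·s0) / s1], where s0 = √(2p̄(1 − p̄)/n_e) and s1 = √([p1(1 − p1) + p2(1 − p2)]/n_e). This is the pooled form. The unpooled form puts s1 in place of s0.

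**Step 1: reproduce 9.2.** For k = 3, n_e = 60 × 3 / (1 + 2 × 0.5) = 90. For 60 vs 79.2%: p̄ = 0.696, s0 = 0.0686, s1 = 0.0671, and (0.192 − 0.1344)/0.0671 = 0.859, so power is 80.5%. The other two pairs give 79.8% and 80.3%. All three reach 80%, so the sum is right for the test that 9.2 describes.

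**Step 2: change only the test.** For k = 2, n_e = 120/1.5 = 80. For k = 1, n_e = 60. For 60 vs 79.2% and k = 1: s0 = 0.0840, s1 = 0.0821, and (0.192 − 0.1646)/0.0821 = 0.334, so power is 63.1%.

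Power at 60 per arm, alpha 0.05 (pooled / unpooled):

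| Pair | 3-visit average (9.2) | 2-visit average | One visit (9.6) |
|---|---|---|---|
| 60 vs 79.2% | 80.5 / 81.7% | 75.7 / 77.0% | 63.1 / 64.7% |
| 70 vs 87% | 79.8 / 81.0% | 74.9 / 76.3% | 62.3 / 63.9% |
| 80 vs 94% | 80.3 / 81.5% | 75.4 / 76.8% | 62.8 / 64.5% |

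**Step 3: possible success rules.** Treat the two visit-specific test statistics as bivariate normal with correlation 0.5. Both significant: 46.5–49.3%. Either significant = 2 × (one) − (both), for example 2 × 0.631 − 0.474 = 0.788; over the pairs, 78–80%. With no true effect, either is significant 9.1% of the time (8.3–9.5% for r from 0.7 to 0.3). That counts one endpoint only, without the weeks-retained test.

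**Step 4: sensitivity**

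| Setting | 2-visit average | One visit |
|---|---|---|
| 60 per arm, alpha 0.025 | 65–68% | 51–54% |
| 75 per arm (no loss), alpha 0.05 | 84–86% | 72–74% |
| 75 per arm, alpha 0.025 | 76–78% | 62–64% |

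One-visit power does not depend on r. The two-visit average at 60 per arm and alpha 0.05 is 81–83% at r = 0.3 and 69–72% at r = 0.7.

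**Step 5: check on the logit scale.** A simulation of 40,000 trials per pair, with correlated binary outcomes, logit contrasts and robust variance (60 per arm, alpha 0.05), gave 60–63% for one visit, 75–76% for the two-visit average, 76–79% for either and 44–48% for both. A closed-form Wald test on the log odds ratio gives 58–62% for one visit.

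**Not affected.** The 0.52 SD figure for weeks abstinent gives 80.6% at 60 per arm and reproduces.

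**The case against.** - **Covariates.** Section 9.6 adjusts for baseline covariates, and the figures above do not. As a rough linear guide, a covariate correlated 0.5 with the outcome would raise 60 to 60/(1 − 0.25) = 80 effective women per arm, or 75–77% for one visit. But the plan does not name the covariates, gives no correlation, and claims no such gain in 9.2. Baseline retention may also carry little information, since every woman is on MOUD at entry. What stands is that the figures should be labelled unadjusted.
- **Choice of test.** A two-proportion test is not a logistic GEE contrast. That is so, but the log-odds figures are lower, so the shortfall is not overstated.
- **No loss of data.** Section 9.3 says "We will use an Intent to Treat model that includes all participants who complete a baseline assessment", and charts may supply outcomes after survey dropout. With all 150 analysed, one visit still has only 72–74%. The two-visit average reaches 84–86%, but 9.6 does not name it, and 9.2 itself allows for 20% loss.
- **Effect pattern.** If the three-visit average included a baseline with no difference, a 19.2-point average would mean 19.2 × 3/2 = 28.8 points after baseline. With 100% retained at baseline that is 40 vs 68.8%, where one visit has about 90% power. Nothing in 9.2 says this, and its 70 vs 87% case is worded as holding at all three visits. The per-visit figures do rest on equal effects.
- **The 9% error rate.** The plan never says that either visit suffices. The figure shows what one permitted reading would cost.
- **Undefined binary outcomes.** Sections 6.2 and 9.5.1 describe the endpoints largely as counts of weeks, with no rule that makes them binary. This is a separate gap, to be closed in the same edit.

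**Conclusion.** The concern holds. The 80% in 9.2 is correctly computed, but for a test that 9.6 does not perform. On the plan's own basis (60 per arm, stated rates at each visit, two-sided 0.05, unadjusted), one named visit has 62–65% power and requiring both has about 47–49%. Allowing either has 78–80%, with about 9% type I error per endpoint. Testing the visits separately is not the whole cause: an average over the two post-randomisation visits also falls short, at 75–77%, because the third visit precedes treatment. The two-visit figure depends on r; the one-visit figure does not. Both binary primary endpoints are affected, so this must be fixed before the data are unlocked.

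**What to change.** **In 9.6.** Name one primary contrast for each binary endpoint. The sponsor can choose either:

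- **A:** the arm effect averaged over the 8-week and 3-month postpartum visits, from the same GEE; or
- **B:** the arm effect at one named visit.

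Make the other contrasts secondary. State whether the weeks-retained test is primary or secondary, and give the multiplicity rule across everything left as primary, for example Holm across the two endpoints.

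**In 9.2.** Replace the three time points with those actually tested. Then restate power at the alpha used, or the MMORE rate detectable with 80% power, labelled as unadjusted:

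| Option, 60 per arm | Power for the stated pairs | Detectable against TAU 60 / 70 / 80% |
|---|---|---|
| A, alpha 0.05 | 75–77% | about 80 / 88 / 94.5% |
| A, alpha 0.025 (first Holm step) | 65–68% | about 82 / 89 / 96% |
| B, alpha 0.05 | 62–65% | about 83 / 90 / 96% |
| B, alpha 0.025 | 51–54% | about 85 / 92 / 97.5% |

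The detectable rates use the pooled formula with r = 0.5.

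**Cost.** Wording in two sections and a less favourable stated power; no extra participants. Keeping 80% for the stated pairs under B at 0.05 would instead need 89–91 evaluable women per arm. If effects are equal at both visits, A keeps about 13 points more power than B (for example 75.7 − 63.1 = 12.6). But A dilutes an effect that appears mainly at 3 months postpartum, and Section 2.1 places the steepest loss from treatment between 6 weeks and 3 months after birth.
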